8.3 ATRA Toxicity

[figure not shown]
Decisions on IMG-7289 and ATRA dose interruption, reduction and re-challenge due to observed toxicity will be made by the Investigator in consultation with Medical Monitor and DSMC.

Expected toxicities for ATRA can be found in the Product Information (PI) document.

CCI

CCI

[figure not shown]

[figure not shown]
CCI

CCI

CCI

CCI

CC

[figure not shown]

CCI

CCI

[figure not shown]

[figure not shown]

CCI

CCI

[figure not shown]

CC

CCI

CCI

CCI

CCI

CCI

CCI

CCI

CCI

10 LABORATORY SAMPLING FOR SAFETY, PK AND PD ANALYSIS

Blood, bone marrow and/or their contents may be retained for future exploratory studies.

The amount of blood collected from each patient for safety, PK and PD assessments will vary by Cohort due to differing PK sampling requirements, treatment durations, and DSMC assessment of biochemistry trends as either clinically significant or not clinically significant. The average of the blood volumes, which vary by institution, is provided below for each cohort.

Sub-cohort 1a: Approximately 539 mL blood over ~15 weeks

Sub-cohort 1b*#: Approximately 478 mL blood over ~15 weeks

Cohort 3/3χ#: Approximately 322 mL blood over ~13 weeks

Cohort 4/4χ#: Approximately 267 mL blood over ~11 weeks

The number of bone marrow aspirates and biopsies, and therefore the total volume required, will vary by Cohort due to differing treatment durations, and the number of Cycles allowed. For each sample time-point, approximately 2-3 mL of bone marrow sample is required. Estimates, by cohort, are provided below.

Sub-cohort 1*: 4 samples and approximately 8-12 mL bone marrow over ~15 weeks

Cohort 3/3χ: 3 samples and approximately 6-9 mL bone marrow over ~13 weeks

Cohort 4/4χ: 3 samples and approximately 6-9 mL bone marrow over ~11 weeks

*Applies to all sub-cohorts.

#Figures based on standard biochemistry evaluations; if clinically significant trends are noted by the DSMC, these numbers will increase by Cohort (1, 3/3χ, or 4/4χ respectively), as follows: 63, 49, and 28 mL.

Note: The above blood volume, and bone marrow sampling time-points and volume, includes all Screening assessments and each study visit up to and including the EOS. Not included, however, are any additional cycles that a patient may be allowed to receive if clinical benefit is observed nor the extended rest period.

10.1 Laboratory Measures

Details on the laboratory assessments performed throughout the study are provided below by category of tests (i.e., biochemistry, haematology with manual differential, etc.). Details on the specific laboratory assessments required at each visit are located in Section 9 and in schematic form in Appendix 16.1. When each category of test is required, at a minimum, the following clinical laboratory determinations (or their equivalent) will be performed.

10.1.1 Local Laboratory Measures

Biochemistry: Sodium, potassium, magnesium, chloride, bicarbonate, glucose, calculated creatinine clearance (by Cockcroft-Gault method) and/or serum creatinine, uric acid, phosphate, total calcium, anion gap, urea or blood urea nitrogen (BUN), triglyceride, cholesterol, albumin, protein, total bilirubin, conjugated (direct) bilirubin, unconjugated (indirect) bilirubin, gamma

glutamyltransferase (GGT), alkaline phosphatase (ALP), alanine aminotransferase (ALT), aspartate transaminase (AST), lactate dehydrogenase (LDH). At specified time-points, Prostate Specific Antigen (PSA) will also be measured in males.

Haematology (with manual differential): Haemoglobin, red blood cell count (RBC) (including nucleated RBC), red cell distribution width (RDW), haematocrit, mean corpuscular volume (MCV), mean corpuscular haemoglobin (MCH), mean corpuscular haemoglobin concentration (MCHC), platelets, mean platelet volume (MPV), immature platelet fraction (IPF), white cell count, neutrophils, lymphocytes, monocytes, eosinophils, basophils, reticulocytes, promyelocytes, myelocytes, blasts and Auer rods. At specified time-points, haemoglobin F (HbF) will also be measured.

Coagulation: Prothrombin time (PT), activated partial thromboplastin time (aPTT) and International normalized ratio (INR).

Urine Pregnancy Test: For WOCBP, a urine pregnancy testing kit will be utilized.

Urinalysis: Leucocyte esterase, nitrites, urobilinogen, protein, pH, blood, specific gravity, ketones, bilirubin, glucose and microscopic examination.

Bone marrow sampling: Aspirate and biopsy samples are to be collected as per site procedure. Evaluation, will be performed centrally (see Section 10.1.2); however, any locally available morphology, immunophenotyping, cytogenetic evaluations/ genetic interrogations performed on samples obtained at the same time-point as study samples, will also be reported in the eCRF.

Sample Processing: Imago BioSciences will not provide either a laboratory manual or study supplies for the collection and handling of samples to be analysed locally – with the exception of urine pregnancy test kits for sites that cannot provide these. Local laboratory standard procedures should be followed at each site.

10.1.2 Central Laboratory Measures

Immunophenotyping - peripheral blood: Fluorescence-activated cell sorting or flow cytometry (FACS; FC), will be performed using 4 mL blood per required time-point. Baseline, end of the dosing period, and EOT and EOS visit peripheral blood samples will be routinely analysed; however, samples collected at other time-points may not be analysed unless the bone marrow sample is inadequate for immunophenotyping (note: sample may also be used for genomic testing if bone marrow sample is inadequate). A standardized panel and gating will be used.

Cytokines: A 8.5 mL blood sample, per required time-point, for cytokine profiles may be quantified, via appropriate methods.

Bone marrow: A 2-3 mL bone marrow sample for central analysis must be collected from the first pull, whenever possible, and no later than the third. A 1-2 cm section of trephine bone marrow sample for central analysis must also be collected. Measures to be performed centrally include: immunophenotyping by FACS or FC, genomic analysis, and morphology review using 5 site prepared slides. Fluorescent *in-situ* hybridization may also be performed, cost permitting. A blood film must also be provided for review in conjunction with the marrow sample. For selected

samples, if the marrow sample is inadequate, then immunophenotyping or genomic testing will be performed using peripheral blood.

Genomic Testing: If there is sufficient sample volume, then approximately 1-2 mL bone marrow aspirate will be used for analysis of mutant allele burden over the course of IMG-7289 treatment; if sample volume is insufficient, then peripheral blood collected for immunophenotyping purposes may be used. At Baseline and EOT, 10 mL blood will be collected for analysis. Genomic sample collection, handling, storage, and analysis will conform to all applicable national guidance and regulations.

Sample Processing: Imago BioSciences will provide a laboratory manual documenting the collection and handling of samples to be analysed centrally. Additional supplies may be provided, dependent on the analyte to be measured and the supplies needed.

CCI

CCI

11 SAFETY

The Investigator is responsible for monitoring the safety of patients who have been enrolled in this study.

Once an Investigator determines a patient is a treatment failure (see Section 6.8) or if the patient is withdrawn from treatment early due to a Dose Limiting Toxicity, the patient should discontinue study treatment and undergo all follow-up procedures, beginning with an End of Treatment Visit (see Section 9.12.1).

11.1 Pregnancy

Every effort should be made to prevent pregnancy throughout the entire duration of participation in this study. All patients of reproductive potential involved in the study are required to use effective methods of contraception during the study and for 28 days after the last IMG-7289 dose. Female patients will be instructed to notify the Investigator immediately if they discover they are pregnant; male patients will be instructed to notify the Investigator immediately if they discover that their sexual partner is pregnant. Pregnancy data during the study will be reported in an expedited manner using the Pregnancy Report Form and following the SAE reporting process (see Section 11.2.4). It will be necessary to collect detailed information on the course of any pregnancy occurring in a patient on study, including pregnancies in the partners of male patients, assuming consent to do so is provided. If the outcome and/or a complication of the pregnancy meets serious criteria (i.e., miscarriage or congenital anomaly/birth defect), then it should be reported as an SAE using the SAE/ MEOI Report Form.

Pregnant patients will discontinue study medication for the duration of the pregnancy. The pregnancy will be followed by the Investigator and the outcome of the pregnancy will be reported to the Pharmacovigilance group as per the Study Reference Manual (SRM).

It is not known whether IMG-7289 can affect reproductive capacity, and the direct effects of IMG-7289 and the indirect effects of prior IMG-7289 exposure on fetal development are also unknown.

It is well documented that ATRA can cause deformities to the unborn fetus. Patients who are taking the combination therapy will be provided with this information.

All patients will be encouraged to discuss contraception and pregnancy concerns with their physician in advance of becoming pregnant. Full disclosure of a patient's participation in this study to their general practitioner is strongly recommended.

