The second phase of the study, the duration-finding phase, will be used to identify the safety and clinical effects of IMG-7289 treatment for durations longer than 7 days as well as provide samples sufficient to establish drug concentrations at steady state, with and without ATRA.

A DSMC review will be conducted after a minimum of 3 patients in a cohort/sub-cohort have completed Cycle 1 to determine the safety of each dose and different treatment durations, with and without ATRA. The DSMC will also assess the impact of each dose on normal myeloid haematopoiesis, the PD impact of that dose on malignant cells, and whether a further cohort/sub-cohort in the respective phase is appropriate. Changes in the clearance of IMG-7289, with and without ATRA, based on drug concentrations at C_{min} will be reviewed as

available. As DSMC review of data continues throughout the study, the DSMC may also recommend a different cohort progression than is currently outlined in the protocol.

Importantly, if a specific dose, treatment regimen or dosing duration is found by the DSMC to be associated with greater therapeutic benefit, patients that have *fully completed* their initially allowed IMG-7289 cycles and are receiving either a different dose, treatment regimen (i.e., IMG-7289 alone *versus* combination therapy) or dosing for a different dosing duration will be transitioned to the more optimal dose, treatment regimen or dosing duration at the start of their next cycle. Such transition may occur more than once, as different doses, treatment regimens and dosing durations continue to be evaluated.

Patients will be followed closely for both Adverse Events (AEs) and signs of toxicity by frequent monitoring of clinical signs and symptoms and by peripheral blood and urine analyses. Pharmacodynamic effects will also be closely monitored by frequent haematology assessments of peripheral blood and bone marrow aspirates and biopsies, as required.

All patients will undergo End-of-Treatment (EOT), pre-End-of-Study (pre-EOS), and End-of-Study (EOS) visits approximately 7, 14 and 28 days, respectively, after last Cycle last dose.

Study Phases, Doses and Duration:

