Additional Cycles: Upon completion of the number of initially allowed IMG-7289 cycles per sub-cohort, patients deriving clinical benefit and safely tolerating IMG-7289, as determined by the Principal Investigator, may continue to receive IMG-7289, with additional dose titration, treatment regimen and/or duration changes occurring in consultation with the Medical Monitor, until disease progression or unacceptable toxicity ensues. During the additional cycle period, the rest period may be extended from the 7 day standard to a maximum of 56 days, but only after: 1) the patient has received a minimum of 28 IMG-7289 doses; and, 2) consultation with or recommendation by the DSMC. Such recommendation may be made for a variety of reasons including evidence of tumour reduction, marked hypocellularity in the marrow consistent with myelosuppression, or to enable the return of normal haematopoiesis. For protocol purposes, a rest period extending beyond the 7 day standard will be referred to as the extended rest period (see Section 9.10).

Patients who either fail to demonstrate stable disease, demonstrate progressive disease after achieving partial remission (PR) or stable disease, or relapse after achieving complete remission (CR), CR with incomplete recovery (CRi) or PR (see **Table 14** and **Table 15**) are the equivalent of treatment failures, and will discontinue study drug and enter the follow-up period.

Study Duration: Screening procedures may commence up to 28 days prior to the start of treatment. Depending on the duration of dosing in each cohort, patients may initially undergo four, three, two or one treatment cycles while on study to a total of approximately 28 days of dosing, with Rest Periods between each cycle anticipated to last approximately 7 days. Patients should be followed for 28 days post last dose. As such, the length of patient participation will vary by cohort. For Cohort 1 this will be ~15 weeks from first patient-first visit (FPFV) to last patient-last visit (LPLV), for Cohort 3/3χ ~13 weeks, and for Cohort 4/4χ ~11 weeks. As described above, additional cycles may be given, contingent on patient response.

CCI

Adverse events (AEs) will be assessed throughout the study after the first IMG-7289 dose to the End of Study visit (EOS). AE frequency, causality, and severity will be evaluated as measures of safety and tolerability. Febrile neutropenia admissions will also be assessed.

CCI

Clinical laboratory measures:

Cycle 1

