Patients who either fail to demonstrate stable disease, demonstrate progressive disease after achieving partial remission (PR) or stable disease, or relapse after achieving complete remission (CR), CR with incomplete recovery (CRi), or PR (see **Table 14** and **Table 15**) are the equivalent of treatment failures, and will discontinue study drug and enter the follow-up period.

Patients will be followed closely for both Adverse Events (AEs) and signs of toxicity by frequent monitoring of clinical signs and symptoms and by blood and urine analyses both during the IMG-7289 treatment period and the rest period. Pharmacodynamic effects will also be closely monitored by frequent haematology assessments of peripheral blood and bone marrow aspirates, as required.

All patients will undergo End-of-Treatment (EOT), pre-End of Study (pre-EOS), and End-of-Study (EOS) visits approximately 7, 14, and 28 days, respectively, after last Cycle last dose.

A detailed description by-cohort, by-cycle, of assessments to be performed is provided in Section 9. Additionally, a by-cohort schema of assessments is included in Section 16.1, Schedule of Assessments.

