6. WBC $\leq 30 \times 10^9/L$ (30,000/ μL) for at least one week prior to first dose, with hydroxyurea use to achieve this value acceptable.
7. Platelet count $\geq 30 \times 10^9/L$ (30,000/ μL) prior to first dose, with transfusions to reach this limit acceptable.
8. Life expectancy >12 weeks.
9. Willing to discontinue all existing anti-neoplastic therapies (with the exception of hydroxyurea) for the 3 weeks prior to first dose of IMG-7289, total duration of dosing, and 1 week after last dose.
10. Amenable to serial bone marrow evaluation, blood, and urine sampling during the study.
11. Able to swallow capsules.
12. Agrees to use an approved method of contraception from Screening and until 28 days after the last administration of the study drug. Agreed methods of contraception may include: condom; use of birth control pills, patches, implants or injections, diaphragm with vaginal spermicide, intrauterine device (IUD) and/or surgical sterilization (vasectomy or tubal ligation at least six months prior to dosing). Patients practicing abstinence must agree to use an approved method of contraception should they become sexually active during the study.

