11.2 Adverse Events

The Investigator is responsible for monitoring the safety of patients who have enrolled in the study and for accurately documenting and reporting information as described in this section. Patients will be instructed to report to the Investigator any AE that they experience. Investigators will ask about the occurrence of AEs at each visit. Investigators are required to document all AEs occurring during the clinical study, commencing with the first dose of IMG-7289 through to the End of Study Visit (scheduled at 28 days post last IMG-7289 dose). Adverse event recording will continue for patients

who discontinue study treatment early but remain in follow-up, until their End of Treatment, Pre-End of Study and End of Study Visits have been completed.

Note: Any medical event which occurs from the time of Informed Consent but prior to dosing with IMG-7289 must still be documented in the patient's medical notes and will be recorded on the appropriate medical history CRF pages.

Adverse events will be recorded on designated CRF pages. Each AE is to be characterised (i.e., verbatim term) and information provided regarding its seriousness, start and stop dates, intensity, outcome, and causal relationship with the study drug.

An AE is any undesirable physical, psychological or behavioral effect experienced by a patient during participation in an investigational study, in conjunction with the use of the drug or biologic, whether or not product-related. This includes any untoward signs or symptoms experienced by the patient from the time of first dose with IMG-7289 until completion of the study.

Adverse events may include, but are not limited to:

- Subjective or objective symptoms spontaneously offered by the patient and/or observed by the Investigator or medical staff
- Findings at physical examinations
- Laboratory abnormalities of clinical significance

Progression of underlying malignancy is not reported as an AE if it is consistent with the suspected progression of the underlying cancer. Clinical symptoms of progression may be reported as AEs if the symptom cannot be determined as exclusively due to the progression of the underlying malignancy or does not fit the expected pattern of progression for the disease under study. If there is any uncertainty about an AE being due to only the disease under study, it should be reported as an AE.

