11.2.3 Serious Adverse Events

Serious adverse events will be reportable from the time the time of first dose through the End of Study Visit (scheduled for approximately 28 days post last IMG-7289 dose) **or** until the Investigator and Imago BioSciences determine that follow-up is no longer necessary. Serious adverse events that are suspected to be drug related will be reported even if they occur when the patient is no longer on the study.

An SAE is any AE that results in any of the following outcomes:

- Death[‡]
- Life-threatening experience
- Required or prolonged inpatient hospitalisation[‡]
- Persistent or significant disability/incapacity
- Congenital anomaly
- Important medical events that, based upon appropriate medical judgment, may jeopardise the patient and may require medical or surgical intervention to prevent one of the outcomes listed above.

Life-threatening experience. Any adverse event that places the patient, in the view of the reporter, at immediate risk of death from the adverse event as it occurred, i.e., does not include an adverse event that had it occurred in a more severe form, might have caused death.

Required or prolonged inpatient hospitalisation. The adverse event resulted in an initial inpatient hospitalisation or prolonged an existing hospitalisation of the patient. If a patient is hospitalised as part of the clinical use of the product, a period of normal hospitalisation will be outlined in the protocol or by the judgment of the Investigator. Hospitalisations longer than this period will be prolonged hospitalisations.

Persistent or significant disability/incapacity. An adverse event that resulted in a substantial disruption of a person’s ability to conduct normal life functions.

Congenital Anomaly. The exposure of the patient to the drug or biologic during pregnancy that is

judged to have resulted in the congenital anomaly/birth defect.

Important medical events. Adverse events that may not result in death, be life-threatening, or require hospitalisation may be considered a serious adverse event when, based upon appropriate medical judgment, may jeopardise the patient or subject and may require medical or surgical intervention to prevent one of the outcomes listed above. Important medical events or interventions may be considered an SAE based upon medical judgment of the Investigator.

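### Section 11.1 times contraception from the last IMG-7289 dose only, so a patient whose ATRA ends later gets less than 28 days of cover after the drug the protocol names as a teratogen

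*Protocol*

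**What the plan says.** Section 11.1 asks patients of reproductive potential to use "effective methods of contraception during the study and for 28 days after the last IMG-7289 dose". It describes the effects of IMG-7289 on fetal development as unknown, and then says of the combination partner: "It is well documented that ATRA can cause deformities to the unborn fetus".

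Inclusion criterion 12, in the synopsis and in Section 6.1.1, uses another anchor. Contraception runs "from Screening and until 28 days after the last administration of the study drug". The visible protocol does not define that term, and its usage points both ways. The synopsis lists IMG-7289 as the investigational drug and ATRA as an additional medication. Section 7.2.3 uses the term above separate subsections for each drug, and SAP X.B (Exposure) uses it for either one.

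The end of follow-up is also anchored in two ways. Section 11.2 records adverse events up to the "End of Study Visit (scheduled at 28 days post last IMG-7289 dose", and Section 11.2.3 does the same for serious events with "End of Study Visit (scheduled for approximately 28 days post last IMG-7289 dose". Section 5.1 instead places the three closing visits, "visits approximately 7, 14, and 28 days, respectively, after last Cycle last dose", without naming the drug. The synopsis and SAP IV.A repeat this, and the synopsis adds: "Patients should be followed for 28 days post last dose".

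**The concern.** The clause that sets the contraception period follows the drug whose fetal effects are unknown and leaves out the drug whose fetal harm is stated as known. This would not matter if both drugs always ended on the same day. In the 21-day ATRA regimen they need not: ATRA runs 21 days on and 7 off, against 7 on and 7 off for IMG-7289.

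Two sites could in good faith tell a patient different end dates, depending on which clause they follow and how they read the study drug. The words 'during the study' in Section 11.1 do not settle it. If End of Study is 28 days after IMG-7289, they add no cover. If it is 28 days after the last dose of any drug, they do. What is at stake is patient safety and consistent instruction. No endpoint or analysis result depends on it.

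**Working it through.** **Inputs**
- Contraception: 28 days after the last IMG-7289 dose (Section 11.1).
- IMG-7289 in the dose-finding phase: 7 days on, 7 off (Section 5.1).
- 21-day ATRA: 21 days on, 7 off (Section 3.7; Section 7.2.2.1, Table 2, Sub-cohort 1w).
- ATRA continues through the IMG-7289 rest week in Cycle 3 (Section 16.1.3, note o) and in every other additional cycle (Section 16.1.8, note h).

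The 28 days is a stated rule, so there is no derived figure to reproduce.

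**General rule.** If ATRA ends g days after IMG-7289, cover after ATRA under Section 11.1 is 28 − g days.

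**Sub-cohort 1w.** Day 1 is the start of Cycle 1, and both drugs start together. The last IMG-7289 day in cycle c is 14(c − 1) + 7. ATRA is taken on Days 1–21 of each 28-day block and, for this calculation, through the rest week where it is scheduled.

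| Final cycle | Last IMG-7289 | Last ATRA | g | 11.1 ends | Days after ATRA |
|---|---|---|---|---|---|
| 1 | Day 7 | Day 14 | 7 | Day 35 | 21 |
| 2 | Day 21 | Day 21 | 0 | Day 49 | 28 |
| 3 | Day 35 | Day 42 | 7 | Day 63 | 21 |
| 4 | Day 49 | Day 49 | 0 | Day 77 | 28 |
| 5 | Day 63 | Day 70 | 7 | Day 91 | 21 |
| 6 | Day 77 | Day 77 | 0 | Day 105 | 28 |

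**Qualifications**
- Odd cycles carry the gap because ATRA began in an odd cycle. A patient moved to this regimen at the start of an even cycle has the gap after even cycles instead.
- For additional cycles, the visible ATRA row in Section 16.1.8 shows six rest-day marks. If ATRA ends on rest day 6, cover is 28 − 6 = 22 days. The missing seventh mark may be an effect of text extraction.
- If ATRA is stopped on the last IMG-7289 day, g = 0 and cover is 28 days after any cycle.

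**Other combination cohorts, default schedules.** ATRA and IMG-7289 durations are equal, so both end on the same day: Day 49 after four cycles in 1χ, Day 35 after two in 3χ, and Day 21 after one in 4χ. Cover is 28 days in each.

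**Pregnancy test.** Section 16.1.1 includes a urine test at End of Study. On the Section 11.2 anchor, that test also falls 21 days after ATRA when g = 7.

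**Scale.** Section 3.4 gives an ATRA half-life of 0.8 hours, so 21 days is 21 × 24 / 0.8 = 630 half-lives. Section 3.7 gives 4–5 days for IMG-7289, so 28 days is 28/5 = 5.6 to 28/4 = 7.0 half-lives. Half-life alone does not settle fetal risk.

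**The case against.** The strongest reply is that the clauses add up rather than conflict. A patient must satisfy both, and if the study drug includes ATRA, criterion 12 already gives 28 days after ATRA. A definition could also sit in the redacted parts of Sections 7 and 9, or in the consent text, neither of which is visible. Combination patients are to be told of the fetal risk (Section 11.1), and each Principal Investigator receives ATRA's Product Information (synopsis). This limits the harm, but it does not alter Section 11.1's explicit IMG-7289 anchor. The inclusive reading is only one of two available.

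IMG-7289 is also much the slower drug to clear, so using it as an anchor is defensible. That stands. It supports keeping 28 days after IMG-7289, which the change below does. It gives no reason to leave ATRA out.

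The gap may also be rare. A stop for treatment failure or dose-limiting toxicity ends study treatment (Section 11), perhaps both drugs together. Within Cycles 2 to 4 of Cohort 1, marrow is scheduled only in Cycles 2 and 4 (Section 16.1.3, note c), where a patient who started ATRA in Cycle 1 has no gap. This stands too, and the number affected cannot be derived. On the other side, the documents do not say when ATRA stops once IMG-7289 is discontinued. Section 8.3 leaves interruption of the two drugs to case-by-case decision, SAP VII.B tabulates premature ending of each separately, and the DSMC may adjust ATRA duration. The gap is therefore not confined to the scheduled case.

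A reader might infer that the plan leaves patients unsafely covered. The documents set no separate ATRA period and do not show that 21 days is too short, so that reading is unsupported.

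**Conclusion.** The point holds as a low-severity safety harmonisation. Section 11.1 alone gives less than 28 days after ATRA whenever ATRA ends later than IMG-7289. In the main scheduled case the shortfall is about 7 days (21 days of cover, or 22 if ATRA ends on rest day 6).

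This rests on three assumptions: the patient is on the 21-day regimen, the final cycle is one with ATRA in the rest week, and ATRA is actually taken through that week. Separate stopping would give a shortfall equal to the interval between the last doses. It would be wrong to conclude that all combination patients are affected, or that a stated standard is breached.

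**What to change.** In Section 11.1 and in both copies of criterion 12 (synopsis and Section 6.1.1), write: 28 days after the last dose of IMG-7289 or ATRA, whichever is later. For combination patients, anchor the End of Study visit in Sections 11.2 and 11.2.3 to the same date, so that its pregnancy test and the collection of adverse and serious adverse events move with it. Moving only the contraception date and the test would leave them running past the end of follow-up. SAP IX.A, which describes adverse event recording as within 28 days of the last IMG-7289 treatment, should follow.

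The cost is up to about 7 more days of contraception and follow-up for a few combination patients. For a Cycle 3 stop this means Day 42 + 28 = Day 70 instead of Day 35 + 28 = Day 63. Section 14.1 requires ethics committee approval of protocol changes, so the wording belongs in the next amendment. The consent text needs a change only if it repeats the IMG-7289 anchor.
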